**Effective**

Version: 2.0

15. Treatment with chemotherapy, immunosuppressive agents, immunomodulatory therapy (e.g. monoclonal antibodies), systemic corticosteroids within 3 months before treatment (inhaled corticoids are allowed).
16. Treatment with topical (facial below the level of the lower orbital rim) retinoids or corticosteroids within 1 month, or systemic retinoids within 6 months before treatment.
17. Any medical condition that in the opinion of the Investigator would make the subject unsuitable for inclusion.
18. Other condition preventing the subject from entering the study in the Investigator's opinion, e.g. subjects not likely to avoid other facial cosmetic treatments, subjects anticipated to be unreliable, unavailable or incapable of understanding the study assessments or having unrealistic expectations of the treatment result.
19. Women who are pregnant or breast feeding, or Woman of childbearing potential who are not practicing adequate contraception or planning to become pregnant during the study period.
20. Subjects planning to accept any other facial plastic surgical or cosmetic procedures below the level of the lower orbital rim during the study (e.g., laser or chemical resurfacing, needling, facelift, radiofrequency etc.).
21. The presence of moderate or severe abnormal rating for midface symmetry, i.e. more than 1 point difference in MMVS score between each side of the face.
22. Intention to change a significant amount of weight ( $\geq 2$  BMI) during the study period.
23. Study site personnel, close relatives of the study site personnel (e.g. parents, children, siblings, or spouse), employees, or close relatives of employees at the Sponsor Company.
24. Participation in any other clinical study within 30 days before treatment.

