2.1 General methods

All summaries for Group A and B will be done separately. The analyses described in the following sections primarily concern Group B. However, Group A will be analyzed in the same way, except that no hypothesis testing will be performed for Group A (there is only one treatment group in Group A), and the analyses will be done based on observed cases (i.e. no imputation of missing values will be done).

All statistical analyses, including summary tables and data listings, will be performed using the SAS® system (version 9.4 or later).

In general, effectiveness, safety, demography, subject characteristics, and treatment related variables will be presented using descriptive statistics. Continuous data will be summarized using n (number of observations), mean, standard deviation, median, minimum and maximum value, while categorical data will be presented by frequency and percentage. Graphs may be used as appropriate.

All statistical testing will be two-sided and performed at a significance level of 5%. Confidence intervals will be 2-sided and constructed using 95% confidence level.

If any SAP changes are needed before database lock (DBL), the SAP will be amended. Changes after DBL will be documented in the Clinical Study Report (CSR). If additional supportive or exploratory analyses are requested after SAP approval, this will not require amendment of the SAP, but these additional analyses will be described in the CSR. Some of the analyses detailed here may be more explicit or in some aspects different from those stated in the protocol. In case of differences, this SAP supersedes the statistical sections in the protocol.

All study data from the CRFs as well as derived variables will be provided in subject data listings.

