2.4.2 Handling of missing data

Different assumptions regarding the missing data will be used. For the primary effectiveness analysis, missing values in the FAS will be assumed to be missing due to lack of effect. Therefore missing data up to the Month 12 visit will be imputed using the baseline observation carried forward (BOCF) method. As an alternative approach, missing data will be assumed to be unrelated to treatment effect. To impute data under this assumption, missing data up to the Month 12 visit will be imputed using the hot deck method. Both of these alternatives will estimate the effectiveness of the treatment policy (irrespective of use of not allowed treatments, procedures, or medications) rather than the true, clinical treatment effect.

To obtain an estimate of the true, clinical treatment effect, the primary effectiveness analysis will be performed using the PP population.

All other endpoints will be analysed on available data (observed cases - OC), i.e. no imputations will be done.

Use of Hot Deck

Each missing value in MMVS at Month 12 visit (recipient) will be imputed with a non-missing (observed) value from a subject randomly selected from the same imputation class (donor). Imputation classes will be defined based on treatment group (Sculptra or Control group), baseline MMVS value (2, 3 or 4 as assessed by the blinded evaluator) and age group (<55 vs. ≥ 55). Alternative imputation classes may be used if deemed necessary.

	Title 43CHSA1803 Statistical Analysis Plan - Sculptra China	Doc id MA-40407
--	---	---------------------------

Effective date: 2019-10-24 08:59

Effective

Version: 1.0

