2.4.3 Primary effectiveness analysis

The percentage of responders (a responder will be defined as a subject with at least 1 point improvement from baseline MMVS on both sides of the face concurrently) will be calculated at 12 months after baseline both in Treatment Group (denoted as π_{12M} Sculptra) and Control Group (denoted as π_{12M} Control) based on the blinded evaluator's assessment.

The null hypothesis $H_0: \pi_{12M}$ Sculptra = π_{12M} Control will be tested against the alternative hypothesis $H_1: \pi_{12M}$ Sculptra $\neq \pi_{12M}$ Control by using a Fisher's exact test at a significance level of 5%. In addition, for each group and also for the difference between the two groups the two-sided 95% confidence intervals around the estimates of the percentage of responders will also be calculated. The treatment will be deemed a success if the p-value for the treatment difference on the primary endpoint is less than 0.05 (i.e. the proportion of responders is statistically significantly larger in the Treatment Group compared to the Control Group).

Subgroup analyses by site will be performed for the primary analysis. The difference in responder rates along with the 95% confidence intervals will be presented for each each site. No formal statistical testing will be carried out for the subgroup analysis.

In addition, to obtain an estimate of the true clinical treatment effect, the primary analysis will be re-run using the PP analysis set.

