2.7 Determination of Sample Size

There are no available clinical data for Sculptra studied under conditions similar to the current study. However, based on what is seen in clinical studies of injectable fillers in the facial areas, it is

 GALDERMA	<small>Title</small> 43CHSA1803 Statistical Analysis Plan - Sculptra China	<small>Doc id</small> MA-40407
---	--	--

2019-10-24 08:59

Effective date:

Effective

reasonable to assume a response rate of at least 60% in the Sculptra Treatment Group at Month 12. For the no treatment Control Group, response rate of 25.8% has been observed in an ongoing clinical trial in China. Based on this, it was assumed that the response rate will be maximum 30% in the no-treatment Control Group at Month 12.

With a sample size of 100 subjects treated with Sculptra and 50 subjects in the no-treatment control group, Fisher's Exact test will have approximately 90% power to detect difference between the anticipated percentage of responders at a 5% significance level (two-sided). To account for 20% drop-outs, approximately 126 will be randomized to the Sculptra group and approximately 63 to the control group.

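### The hot-deck rule in SAP 2.4.2 does not keep the two sides of a face together or class asymmetric faces, although response requires both sides

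*SAP*

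**What the plan says.** The blinded evaluator rates the right and left midface separately on the MMVS (SAP 1.3.1), so a subject without a Month 12 assessment lacks two scores. The primary endpoint is a property of the whole face: "at least 1 point improvement from baseline MMVS on both sides of the face concurrently" (SAP 2.4.3).

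In the FAS, the primary analysis fills missing Month 12 data by BOCF. The alternative, which assumes that missingness is unrelated to treatment effect, is a hot deck (SAP 2.4.2): "Each missing value in MMVS at Month 12 visit (recipient) will be imputed with a non-missing (observed) value from a subject randomly selected", the donor being in the same class as the recipient. A class is formed by treatment group, age group (under 55, or 55 and over) and "baseline MMVS value (2, 3 or 4 as assessed by the blinded evaluator"). The paragraph does not mention sides. It adds that other classes may be used if that is judged necessary.

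Protocol 5.3, exclusion 21, bars only subjects with "more than 1 point difference in MMVS score between each side of the face", so faces graded 2/3 or 3/4 at baseline are eligible. Protocol 10.6 leaves the imputation details to the SAP.

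The hot-deck result is the third block of SAP Table 3-19, beside the BOCF and per-protocol results.

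**The concern.** The rule is written for a single MMVS value with a single baseline grade, but the endpoint needs a pair of values from one face. A programmer must choose between two readings, and each has a gap.

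- **One draw per missing score.** The two sides of a recipient can come from different people. The pairing within a face is lost, and the chance that both sides improve becomes the product of the two side-level rates. That is too low whenever the sides are positively correlated within a class, which is to be expected for two halves of one face under one treatment and one evaluator.
- **One draw per subject.** Pairing is kept, but a 2/3 or 3/4 face has no single baseline grade and therefore no class. Copying raw scores also needs matching baselines. A 2/3 donor who scores 1/2 at Month 12 is a responder; the same scores given to a 2/2 recipient make a non-responder, because the second side has not moved.

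This is the only imputation of the primary endpoint offered as an alternative to BOCF. Under its own assumption, imputed subjects should respond at the rate of comparable observed subjects. With separate donors they would not, and the row would no longer show what it is meant to show.

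**Working it through.** **Inputs from the plan.** Both-sides response J: "reasonable to assume a response rate of at least 60% in the Sculptra Treatment Group at Month 12", and "the response rate will be maximum 30% in the no-treatment Control Group at Month 12" (SAP 2.7). Randomized 126 and 63, drop-out 20%, Fisher's exact test, two-sided 5%.

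**The plan's own figures first.** With 100 and 50 subjects at 60% and 30%, exact enumeration of Fisher's test gives 92.7% power and an arcsine approximation with continuity correction gives 91.8%, against a stated 90% or so. Drop-out: 100/0.8 = 125 and 50/0.8 = 62.5, rounded up to 63; the plan has 126 (2 × 63) and 63. The design figures hold.

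**Assumed, because the documents do not give it.** D is the share of subjects who improve on one side only, split equally between right and left; range 0-20%. The classes are taken to explain none of the left-right correlation.

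**Formulas.**
- Side-level rate: s = J + D/2.
- Imputed both-sides response: s² with separate donors, J with one donor for both sides.
- Arm rate with missing share d: J(1 − d) + d·s².

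**Equal missingness, d = 20% in both arms, separate donors.**

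| D | Imputed, Sculptra | Imputed, control | Arm rate, Sculptra | Arm rate, control | Difference |
|---|---|---|---|---|---|
| 0 | 0.60² = 36% | 0.30² = 9% | 0.48 + 0.2 × 0.36 = 55.2% | 0.24 + 0.2 × 0.09 = 25.8% | 29.4 |
| 10% | 0.65² = 42% | 0.35² = 12% | 56.45% | 26.45% | 30.0 |
| 20% | 0.70² = 49% | 0.40² = 16% | 57.8% | 27.2% | 30.6 |

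One donor for both sides gives 60%, 30% and 30 points in every row. Separate donors lower the Sculptra rate by 2.2 to 4.8 points and the control rate by 2.8 to 4.2. In a simulation of 20,000 trials (126/63, 20% missing, no classes), power was 95.1% to 96.2% with separate donors and about 95% with one donor.

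**Unequal missingness, D = 10%, separate donors.**
- 10% missing on Sculptra, 30% on control: (0.54 + 0.1 × 0.4225) − (0.21 + 0.3 × 0.1225) = 58.2% − 24.7%, about 34 points.
- 30% and 10%: (0.42 + 0.3 × 0.4225) − (0.27 + 0.1 × 0.1225) = 54.7% − 28.2%, about 26 points.
- One donor: 30 points in both cases.
- BOCF: 54% − 21% = 33 points, and 42% − 27% = 15 points.

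**Where the direction turns.** s² equals J when D = 2(√J − J): about 35% for J = 60% and 50% for J = 30%. Below those values separate draws lower the imputed rate; above them they raise it (D = 40% gives 0.80² = 64% on Sculptra).

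**The case against.** A reader might infer that the SAP prescribes independent draws for the two sides. It does not. The hot-deck paragraph never mentions sides, and the value is taken from a randomly selected subject, so copying that subject's two scores together would not contradict it. The text permits separate donors but does not require them. The sentence allowing other classes would also let an analyst accommodate 2/3 and 3/4 faces. Both points stand. They make this a gap in the rule rather than a stated wrong method. They do not close the gap, because the choice of donor unit and class is left to discretion instead of being pre-specified.

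A reader might also infer that imputed subjects would respond far too rarely. That depends on left-right concordance, which the documents do not report. If response varies across classes, the class-level products average to more than the overall product, so the shortfall is smaller than the table shows.

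A third objection is that little depends on this row. Success is judged on the primary p-value, and no decision rule is attached to the hot deck. The plan allows for 20% drop-out without an arm difference, so the 10%/30% splits are hypothetical. Even with them, expected counts rounded to whole subjects in 126 and 63 give Fisher p-values of about 0.00003 and 0.0007 with separate donors, against 0.0001 with one donor: the same conclusion at the plan's rates. This also stands and limits the weight of the point. What remains is that with more drop-out on control (10%/30%), separate donors give about 34 points beside 33 for BOCF, so the check would seem to confirm BOCF while sharing its distortion. Unequal drop-out is conceivable, since subjects know their assignment and controls receive no treatment.

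**Conclusion.** The point holds as a defect in the specification of the alternative analysis. The rule is written per value and keyed to one baseline grade, while the endpoint is bilateral. One reading loses the pairing of the sides; the other leaves eligible asymmetric faces without a class.

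Under the separate-donor reading, with 0-20% of subjects improving on one side only and classes that explain none of the correlation (both assumed), imputed response is 36-49% instead of 60% on Sculptra and 9-16% instead of 30% on control. At 20% missing in both arms, each rate drops by about 2-5 points and the difference stays between 29.4 and 30.6. Only unequal drop-out moves it materially, to about 34 or 26 points in the example.

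The documents do not support the inference that the treatment effect is generally biased, or that the primary result is at risk: BOCF remains primary and the success rule does not use the hot deck. The rule should be settled before database lock, but it does not threaten the trial's main conclusion.

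**What to change.** In SAP 2.4.2, state that each recipient gets one donor, who supplies the result for both sides together. Bilateral responder status is preferable to raw scores, because donor and recipient baselines then need not match exactly and it does not matter which side carries the worse grade. Define the class by treatment group, age group and the unordered pair of baseline grades (2/2, 2/3, 3/3, 3/4, 4/4). Set a minimum number of donors and a collapse rule in advance, for example to the worse-side grade, in place of the open permission to use other classes.

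The cost is a short SAP amendment and a small programming change. The drawback is sparser classes: five pairs by two age groups make ten per arm, so about 50 observed controls would average five donors each, with fewer in asymmetric or grade-4 classes. The collapse rule would be used often.

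The change does not address the understated variance from analysing one imputed data set as if it were observed. With 30% response in both arms and 20% missing, the same simulation set-up rejected in about 9% of trials with one donor for both sides and about 7% with separate donors. That is a separate matter and needs its own remedy.

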2.4.3 Primary effectiveness analysis

The percentage of responders (a responder will be defined as a subject with at least 1 point improvement from baseline MMVS on both sides of the face concurrently) will be calculated at 12 months after baseline both in Treatment Group (denoted as π_{12M} Sculptra) and Control Group (denoted as π_{12M} Control) based on the blinded evaluator's assessment.

The null hypothesis $H_0: \pi_{12M}$ Sculptra = π_{12M} Control will be tested against the alternative hypothesis $H_1: \pi_{12M}$ Sculptra $\neq \pi_{12M}$ Control by using a Fisher's exact test at a significance level of 5%. In addition, for each group and also for the difference between the two groups the two-sided 95% confidence intervals around the estimates of the percentage of responders will also be calculated. The treatment will be deemed a success if the p-value for the treatment difference on the primary endpoint is less than 0.05 (i.e. the proportion of responders is statistically significantly larger in the Treatment Group compared to the Control Group).

Subgroup analyses by site will be performed for the primary analysis. The difference in responder rates along with the 95% confidence intervals will be presented for each each site. No formal statistical testing will be carried out for the subgroup analysis.

In addition, to obtain an estimate of the true clinical treatment effect, the primary analysis will be re-run using the PP analysis set.

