## 7.3 Medicis Midface Volume Scale (MMVS)

MMVS is a Four-Point scale assesses the fullness of the midface from Fairly Full (1) to Substantial Loss of Fullness (4) as described below. A validation study concluded that the accuracy of this assessment tool was acceptable for use in assessing correction of midface volume loss and/or contour deficiency. The blinded evaluator will rate the subject's right and left midface for severity of volume deficiency using the MMVS at screening, baseline, 6, 9, 12, 18 and 24 months in Group A and Treatment Group, and at screening, baseline 6, 9 and 12 months in Control Group. The treating investigator will do the MMVS evaluation at all visits in each group. The blinded evaluator and treating investigator will conduct their MMVS assessments using a photographic scale (Appendix 2).

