1.1.2 Number of subjects and randomization

The study will be performed at approximately 8 sites in China and approximately 32 subjects in Group A and 189 subjects in group B will be enrolled. Approximately 189 subjects in group B will be randomized in a 2:1 ratio to treatment with Sculptra (Treatment Group) or to no treatment (Control Group). The randomization list will be stratified by site.

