2.4 Effectiveness analysis

2.4.1 Datasets analyzed

All effectiveness variables will be analyzed using the FAS population. The primary analysis will be repeated using the PP population. If it is deemed necessary, other analyses will be repeated using the PP population.

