**Table 3-16: Subjects reporting concomitant medication, FAS**

	Sculptra N = XX				Control N = XX			
	No		Yes		No		Yes	
	n	%	n	%	n	%	n	%
Ongoing at study start								
Initiated during study								
Total								

 $\% = (n/N)*100$

Note: A single subject might have had concomitant medication ongoing at study start and initiated during study

Table 3-17: Subjects reporting concomitant medication and number of medications by reason, FAS

Reason for concomitant medication	Sculptra N = XX				Control N = XX			
	Subjects		Number of medications		Subjects		Number of medications	
	n	%	Total	Ongoing at study end	n	%	Total	Ongoing at study end
Related Adverse Event								
Unrelated Adverse Event								
Medical History								
Other								
Total								

 $\% = (n/N)*100$

Note: A single subject might have reported concomitant medication for several reasons

Table 3-18: Subjects reporting concomitant medication and number of medications by ATC code, FAS

ATC code	ATC text	Sculptra N = XX		Control N = XX		
		Subjects		Number of medications	Subjects	
		n	%		n	%
	Total					

$\% = (n/N) * 100$

Note: A single subject may have reported several types of concomitant medication

Concomitant procedures

In a similar way as for conmed

Efficacy

Table 3-19: MMVS responder rate at Month 12 by treatment (both sides of the face combined), Blinded Evaluator

Population	Visit	Treatment	Subjects		Responders		95% Confidence interval			p-value
			N	n	n	%				
FAS ¹⁾	Month 12	Sculptra								
		Control								
		Difference								
PP ²⁾	Month 12	Sculptra								
		Control								
		Difference								
FAS ³⁾	Month 12	Sculptra								
		Control								
		Difference								

1) Note: Missing values at Month 12 are imputed using the BOCF method.

2) No imputation is used for PP analysis. Only subjects with complete data are included.

3) Note: Missing values at Month 12 are imputed using the Hot deck imputation method.

Note: Responder is defined as a subject with an improvement of at least one grade on the MMVS from baseline

Note: Responder rate (%) = $(n/N) * 100$

Note: P-values for the difference in proportions are based on the Fisher's Exact test.

Note: 95% confidence intervals are two-sided and calculated using the exact interval. For the difference, asymptotic confidence limits are used.

 GALDERMA	Title 43CHSA1803 Statistical Analysis Plan - Sculptra China	Doc id MA-40407
--	---	---------------------------

2019-10-24 08:59

Effective date:

Effective

Version: 1.0

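### Randomisation is stratified by site, but no planned analysis combines the sites into a site-adjusted overall estimate or test: the primary test is valid, and only precision may be lost

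*SAP*

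**What the plan says.** On allocation, SAP 1.1.2 says: "The randomization list will be stratified by site". Protocol 4.4.1 agrees. Site is the only stratification factor, and no block size is given.

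On the primary analysis, SAP 2.4.3 and Protocol 10.4 compare the Month 12 responder proportions "by using a Fisher's exact test at a significance level of 5" per cent, with no stratification. The notes to SAP Table 3-19 add: "For the difference, asymptotic confidence limits are used".

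The repeats do not bring site in:

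- Per protocol (SAP 2.4.1): "The primary analysis will be repeated using the PP population".
- Hot deck (SAP 2.4.2): "Imputation classes will be defined based on treatment group (Sculptra or Control group), baseline MMVS value", plus age group. Site is not among the classes, although the section allows others if needed.
- Observed cases at Month 12 (Table 3-20): again Fisher's test.

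Site appears once in the effectiveness analysis, as a descriptive subgroup in SAP 2.4.3: "The difference in responder rates along with the 95% confidence intervals will be presented for each each site". No formal test accompanies it.

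On power, SAP 2.7 says: "Fisher's Exact test will have approximately 90% power to detect difference between the anticipated percentage of responders", for 100 and 50 subjects at 60% and 30%.

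**The concern.** An analysis normally follows the randomisation. If responder rates differ between sites and allocation is balanced within site, a pooled comparison leaves shared site variation in the error term. The interval for the difference can then be wider than the design requires.

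The subgroup display does not fill the gap. With about 8 sites it rests on roughly 126/8 = 15.8 against 63/8 = 7.9 subjects per site if sites are equal. Eight wide intervals can show heterogeneity, but they do not give one adjusted estimate. Protocol 2.5 intends the study for registration, so whether the result holds after adjustment for the only stratification factor is a predictable question. It is better answered by an analysis named in advance.

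**Working it through.** **1. The plan's own power figure.** Inputs are from SAP 2.7: 100 and 50 subjects, 60% and 30%, two-sided 5%. Power is the sum of Bin(x; 100, 0.60) × Bin(y; 50, 0.30) over all (x, y) with Fisher p < 0.05. Full enumeration gives 92.7%, so the stated figure of about 90% is met.

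Dropout inflation: 100/0.8 = 125 and 50/0.8 = 62.5, rounded up to 63; 2 × 63 = 126. This fits the stated 126 and 63.

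Under BOCF a missing subject is a non-responder. With 20% missing in both arms the rates become 0.8 × 60 = 48% and 0.8 × 30 = 24%. Fisher's power at 126 versus 63 is then 88.9% (97.6% with complete data). Type I error at 30% in both arms is 4.1%.

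**2. Formulas for precision.** In site k let `t`, `c` be the arm sizes, `x`, `y` the responders and `N = t + c`.

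- Unadjusted width: `2 × 1.96 × sqrt[p1(1−p1)/126 + p0(1−p0)/63]`. At 48% and 24% the variance is 0.001981 + 0.002895 = 0.004876, so the width is 3.92 × 0.0698 = 0.274.
- Mantel-Haenszel difference: `RD = Σ[(xc − yt)/N] / Σw`, with `w = tc/N`.
- Sato variance: `(RD·ΣP + ΣQ)/(Σw)²`, with `P = [t²y − c²x + tc(c−t)/2]/N²` and `Q = [x(c−y) + y(t−x)]/(2N)`.

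Take equal sites with exact 2:1 within site and insert expected values:

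- Σw = 126 × 63/189 = 42.
- ΣP = (63/9)(4 × 0.24 − 2 × 0.48 − 1) = −7.
- ΣQ = 21[0.48 + 0.24 − 2(0.1152 + C)] = 10.2816 − 42C, where C is the covariance across sites between the two arms' responder probabilities.
- Variance = (0.24 × (−7) + 10.2816 − 42C)/42² = 0.004876 − C/42.

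With C = 0 this equals the unadjusted variance. Stratification therefore narrows this interval only as far as the arms rise and fall together across sites.

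**3. Size, under stated assumptions.** The documents give no between-site variance. Assume logit-normal site effects with SD 0, 0.5 or 1. SD 1 is extreme: the central 80% of sites would have control rates of 9% to 57% around 30%. For effects common to both arms, integration gives a covariance of 0.0103 at SD 0.5 and 0.0326 at SD 1. Among eight sampled sites the expected covariance is 7/8 of that, so C = 0.0090 and 0.0285. The variances become 0.004662 and 0.004198, and the ratios 1.046 and 1.16.

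Simulation agrees (126 versus 63, 48/24, eight near-equal sites, about 2:1 within site, 40,000 trials per scenario):

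| Site effects | Unadjusted width, SD 0 / 0.5 / 1 | Mantel-Haenszel width | Squared ratio |
|---|---|---|---|
| Common to both arms | 0.272 / 0.271 / 0.269 | 0.272 / 0.265 / 0.249 | 1.00 / 1.05 / 1.17 |
| Treated arm only | 0.272 / 0.271 / 0.270 | 0.272 / 0.271 / 0.270 | 1.00 / 1.00 / 1.00 |
| Independent by arm | 0.272 / 0.271 / 0.269 | 0.272 / 0.271 / 0.269 | 1.00 / 1.00 / 1.00 |

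In the common-effects case with permuted blocks of 6, the Sato interval covers the difference in the study's own sites 94.5 / 94.6 / 94.6% of the time. For a wider population of sites coverage is 94.5 / 94.2 / 92.9%, so the narrower interval speaks for the study sites.

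**4. The test, exact against exact, common site effects.** Type I error at 30/30 with about 2:1 within site: Fisher 4.1 / 3.6 / 2.8%, exact stratified test 4.1 / 4.0 / 3.9% (12,000 trials). Power change at 48/24, stratified minus Fisher: +0.1 / +0.9 / +2.8 points with exact 2:1 within site, and −1.1 / +0.1 / +3.3 points if allocation is not blocked.

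**The case against.** The strongest reply is that nothing is wrong. The test is fixed in advance, holds its level, and is the test for which the sample size was computed. If it stays primary, an added analysis changes neither the power nor the type I error of the success decision. The protocol also limits site differences, through a common photographic scale (7.3) and sponsor review of injection technique before Group B starts (4.1). Site differences will be displayed anyway, and SAP 2.1 allows further supportive analyses without an amendment. Most of this stands and sets the severity.

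It does not remove the gap. The per-site results are not combined, and an analysis added after SAP approval under SAP 2.1 may be chosen with results in view.

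A reader might infer three stronger things, none of which the documents support:

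- **That ignoring the stratum inflates false positives.** Fisher's type I error stays below 5% in every scenario, about 4% if allocation is unblocked and lower if it is blocked and sites differ.
- **That the plan wastes a known number of subjects.** The 5% and 17% gains would correspond to about 9 (189 × 0.047) and 32 (189 × 0.168) of 189 subjects, but only if site effects are common to both arms. Variation in the treated arm alone is also plausible, since the number of sessions and vials follows investigator judgement (Protocol 4.1 and 6.7.2). The gain is then nil.
- **That the gap between Fisher and an asymptotic Cochran-Mantel-Haenszel test near 5% is the price of pooling.** Part of it is the discreteness of exact tests: the exact stratified test also runs at about 4%.

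**Conclusion.** The point holds as a minor one. Site is the only randomisation stratum, and no site-adjusted overall estimate or test is planned. The primary test is valid and adequately powered under the plan's own assumptions.

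The possible loss is precision: about 0 / 5 / 17% at an assumed site SD of 0 / 0.5 / 1 if both arms share the site effects, and about 0% otherwise. These figures assume eight near-equal sites, near 2:1 balance within site, and 48% versus 24% after BOCF. The omission is certain from the text. Its cost cannot be settled from the documents, because neither the between-site variance nor the block size is stated.

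**What to change.** In SAP 2.4.3, pre-specify one site-stratified analysis of the primary endpoint on the FAS with BOCF: a Cochran-Mantel-Haenszel or exact stratified test by site, with the Mantel-Haenszel risk difference and its 95% confidence interval using the Sato variance. Add a matching row to Table 3-19. Add a rule for pooling sites with an empty arm, fixed before database lock and blind to outcome. State the block size in the report.

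Fisher's test may stay primary. The gain is then a supportive site-adjusted estimate and interval, and the success decision is unchanged. The cost is one paragraph, one table row and a few lines of SAS, with no extra subjects or data. SAP 2.1 provides for amendment before database lock and gives the SAP precedence over the protocol's statistical sections, so no protocol change is needed.

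Making the stratified test primary is optional. Only that would alter the power and type I error of the decision, and it would require aligning the protocol synopsis, Protocol 10.4 and 10.10, and SAP 2.4.3 and 2.7.
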